4.1.3. General Considerations for Safety Analyses for Combined Induction and Maintenance Periods

Adverse event, exposure summary, and categorical laboratory/vital signs changes will be provided for the All Lebrikizumab Safety Population during the Combined Induction and Maintenance Periods. For participants who were first exposed to lebrikizumab during the Induction Period, the baseline for TEAE will utilize the baseline for the Induction Period defined in Section 4.1.1; for participants who were first exposed to lebrikizumab during the Maintenance Period, the baseline for TEAE will utilize the baseline for the Maintenance Period defined in Section 4.1.2.

More details on baseline and post-baseline definitions can be found in the Compound Level Safety Standard.

4.1.4. General Considerations for Safety Analyses for Combined Induction and Maintenance Periods Plus Follow-Up Period

Selective AE summaries will be provided for the All Lebrikizumab Safety Population during the Combined Induction and Maintenance Periods plus Follow-Up Period. The baseline definition

for this population is the same as Section 4.1.3. More details on baseline and post-baseline definitions can be found in the Compound Level Safety Standard.

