Intent-to-Treat (ITT)	All randomized participants, even if the participant does not take the assigned treatment, does not receive the correct treatment, or otherwise does not follow the protocol. Participants will be analyzed according to the treatment group to which they were assigned. Unless otherwise specified, efficacy and health outcome analyses for the Induction Period will be conducted on this population.
Safety Population	All randomized participants who received at least 1 dose of study intervention during the Induction Period. Safety analyses for the Induction Period will be conducted on this population.
Per-Protocol Set (PPS)	All ITT participants who do not have a subset of important protocol deviations that impact the primary efficacy endpoint. Important protocol deviations are defined in a separate document referred to as "The KGAL Trial Issues Management Plan." Primary efficacy analysis for IGA score of 0 or 1 and EASI-75 will be repeated using the PPS.
Maintenance Primary Population (MPP)	All participants who were randomized to lebrikizumab 250 mg Q2W or lebrikizumab 250 mg Q4W at baseline visit (Visit 2, Week 0) and met the response criteria (that is, participants who achieved an IGA score of 0 or 1 and/or EASI-75 at Week 16) and received at least 1 dose of study intervention during the Maintenance Period. Participants will be analyzed according to the treatment to which they were assigned. Only information prior to entering the Escape Arm will be presented. Efficacy, health outcome, and safety analyses for the Maintenance Period will be conducted primarily on the MPP.
Maintenance Secondary Population (MSP)	Participants who were randomized to placebo at baseline visit (Visit 2, Week 0) and continued placebo (that is, participants who achieved an IGA score of 0 or 1 and/or EASI-75 at Week 16) and received at least 1 dose of study intervention during the Maintenance Period. Only information prior to entering the Escape Arm will be presented. Selective efficacy analyses for the Maintenance Period will be conducted on the MSP.

Maintenance W16 Escape Population	Participants who moved to the Escape Arm at Week 16 (either due to not meeting IGA and EASI criteria, or used rescue therapy during the Induction Period), and received at least one dose of study intervention during the Maintenance Period. Selective efficacy analyses for the Maintenance Period will be conducted on the Maintenance W16 Escape Population.

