Maintenance W20-64 Escape Population	Participants in MPP or MSP who escaped to lebrikizumab 250 mg Q2W due to EASI-50 non-response at Weeks 20, 24, 28, 32, 36, 40, 44, 48, 52, 56, 60 or 64. Selective efficacy analyses for the Maintenance Period will be conducted on the Maintenance W20-64 Escape Population to assess whether these participants re-gain EASI-50 response or achieve a higher level of response (for example, EASI-75) following re-treatment.
All Maintenance Population	Participants who entered the Maintenance Period and received at least one dose of study intervention during the Maintenance Period.
All Lebrikizumab Safety Population	All randomized participants who received at least 1 dose of lebrikizumab treatment during the Combined Induction and Maintenance Periods including participants who were randomized to placebo at baseline visit (Visit 2, Week 0) and moved to the Escape Arm at Week 16 or later visits in the Maintenance Period. Safety analyses for the Combined Induction and Maintenance Periods will be conducted on the All lebrikizumab Safety Population. Selective safety analyses for the Combined Induction and Maintenance Periods plus the Follow-Up Period will be conducted on the All Lebrikizumab Safety Population.
Pharmacokinetic Analysis	All participants who received at least 1 dose of lebrikizumab and have at least 1 evaluable PK sample.

Abbreviations: EASI-75 = $\geq 75\%$ reduction from baseline in Eczema Area and Severity Index IGA = Investigator's Global Assessment; Q2W = every 2 weeks; Q4W = every 4 weeks; W = Week.

Treatment Groups and Comparisons for Each Study Period and Analysis Population

Study Period	Analysis Population	Treatment Groups	Abbreviation	Inferential Comparisons When Applicable
Induction Period	ITT; Safety; PPS	Placebo; Lebrikizumab 250 mg Q4W; Lebrikizumab 250 mg Q2W; Total	PBO; LEB250Q4W; LEB250Q2W; Total	LEB250Q4W vs PBO; LEB250Q2W vs PBO
Maintenance Blinded Period	MPP	Lebrikizumab 250 mg Q4W_Res/ Lebrikizumab 250 mg Q4W; Lebrikizumab 250 mg Q2W_Res/ Lebrikizumab 250 mg Q4W; Lebrikizumab 250 mg Q2W_Res/ Lebrikizumab 250 mg Q2W; Total	LEB250Q4W_Res/ LEB250Q4W; LEB250Q2W_Res/ LEB250Q4W; LEB250Q2W_Res/ LEB250Q2W; Total	No Between-Group or Overall Comparisons
Maintenance Blinded Period	MSP	Placebo_Res/Placebo	PBO_Res/PBO	No Between-Group or Overall Comparisons

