Maintenance Escape Period	Maintenance W16 Escape Population	Placebo_NonResp/Lebrikizumab 250 mg Q2W; Lebrikizumab 250 mg Q4W_NonResp/Lebrikizumab 250 mg Q2W; Lebrikizumab 250 mg Q2W_NonResp/Lebrikizumab 250 mg Q2W; Total	PBO_NonResp/ LEB250Q2W; LEB250Q4W_NonResp/ LEB250Q2W; LEB250Q2W_NonResp/ LEB250Q2W; Total	No Between-Group or Overall Comparisons

Maintenance Escape Period	Maintenance W20-64 Escape Population	Placebo/Placebo/Lebrikizumab 250 mg Q2W; Lebrikizumab 250 mg Q4W/ Lebrikizumab 250 mg Q4W/ Lebrikizumab 250 mg Q2W; Lebrikizumab 250 mg Q2W/ Lebrikizumab 250 mg Q4W/ Lebrikizumab 250 mg Q2W; Lebrikizumab 250 mg Q2W/ Lebrikizumab 250 mg Q2W/ Lebrikizumab 250 mg Q2W; Total	PBO/PBO/LEB250Q2W; LEB250Q4W/ LEB250Q4W/ LEB250Q2W; LEB250Q2W/ LEB250Q4W/ LEB250Q2W; LEB250Q2W/ LEB250Q2W/ LEB250Q2W;	No Between-Group or Overall Comparisons
Combined Induction and Maintenance Periods	All Lebrikizumab Safety Population	Any Lebrikizumab	N/A	No Between-Group or Overall Comparisons
Combined Induction and Maintenance Periods + FU	All Lebrikizumab Safety Population	Any Lebrikizumab	N/A	No Between-Group or Overall Comparisons

Abbreviations: FU = follow-up; ITT = intent-to-treat; LEB = lebrikizumab; NonResp = non-responder; PBO = placebo; PPS = per protocol set; Q2W = every 2 weeks; Q4W = every 4 weeks; Res = responder.

4. Statistical Analyses

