4.1.2. General Considerations for Analyses During Maintenance Period

Maintenance Period starts at the first injection of study intervention at Week 16 and ends on the date of Week 68 or the ETV (between Weeks 16 and 68) unless specified otherwise.

For the efficacy and health outcome analyses, baseline is defined as the last available value before the first injection in the Induction Period and, in most cases, will be the value recorded at Baseline Visit (Visit 2, Week 0).

Unless otherwise specified, efficacy and health outcome variables at Week 16 prior to entering the Maintenance Period will be presented for the visit-wise reports for the Maintenance Period.

Unless specified otherwise, for the safety analyses during the Maintenance Period, baseline is defined as the last available value before the first injection in the Maintenance Period. In most cases, this will be the measure recorded at Week 16. For TEAEs, baseline is the events ongoing just prior to the first injection of the study drug injection at Week 16.

For participants in the MPP and MSP who met escape criteria (EASI-50 non-response) and escaped to lebrikizumab 250 mg Q2W at Weeks 20, 24, 28, 32, 36, 40, 44, 48, 52, 56, 60 and 64, only data in the Maintenance Blinded Period (up to the time of escape) will be included in both efficacy and safety analyses.

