- Mean and median total dose: Total dose (in mg) is calculated by the number of active injections taken during the treatment period multiplied by dose. For participants in the Safety Population who were randomized to lebrikizumab 250 mg Q4W or Q2W, or participants in the MPP who received lebrikizumab 250 mg Q4W or Q2W, the total dose (in mg) taken during the Induction Period or the Maintenance Period will be calculated as follows: *Total lebrikizumab dose=Total number of active injections (including loading doses, if any) received in the Induction Period or the Maintenance Period ×250.*
- Total number of injections received will be derived based on the response to the question “Was dose administered?” on the *Exposure as Collected* eCRF page.

The exposure for the All Lebrikizumab Safety Population during the Combined Induction and Maintenance Periods will be calculated as (Date of last study visit during Treatment Period – Date of first lebrikizumab injection +1 day) calculated for each treatment period where the participant receives lebrikizumab and then summed together (this excludes the duration of time that participants are receiving placebo during the Maintenance Period).

The exposure for the All Lebrikizumab Safety Population during the Combined Induction and Maintenance Periods plus Follow up Period will be calculated as the time between the first dose of lebrikizumab and the study treatment disposition visit plus any follow-up period.

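### The TEAE baseline for the All Lebrikizumab Safety Population stays at Week 16 for placebo responders first given lebrikizumab at Weeks 20–64, so events arising on placebo can be counted as lebrikizumab TEAEs

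*SAP*

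**What the plan says.** Four parts of the SAP bear on this.

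- **Who is in the population.** Placebo participants who respond at Week 16 stay on blinded placebo. SAP Section 3 defines the Maintenance Secondary Population (MSP) around them: "Participants who were randomized to placebo at baseline visit (Visit 2, Week 0) and continued placebo". If they lose EASI-50 at any visit from Week 20 to Week 64 they move to open-label lebrikizumab, and Section 3 lists them in the W20-64 Escape Population as "Placebo/Placebo/Lebrikizumab 250 mg Q2W". They then belong to the All Lebrikizumab Safety Population, which takes in placebo participants who "moved to the Escape Arm at Week 16 or later visits in the Maintenance Period". That population is reported as one pooled group with no comparisons.
- **TEAE baseline.** Section 4.1.3 says that "for participants who were first exposed to lebrikizumab during the Maintenance Period, the baseline for TEAE will utilize the baseline for the Maintenance Period". Section 4.1.2 supplies the definition: "For TEAEs, baseline is the events ongoing just prior to the first injection of the study drug injection at Week 16". It also says that the "Maintenance Period starts at the first injection of study intervention at Week 16", whichever product is injected. Section 4.1.4 adopts the same baseline for the analysis that adds follow-up.
- **What counts as treatment-emergent.** Section 4.6.2 counts an event that is new or worse after baseline and uses the Treatment Period as the post-baseline period.
- **Exposure.** For the same population, Section 4.6.1 counts from the first lebrikizumab injection and notes that "this excludes the duration of time that participants are receiving placebo during the Maintenance Period".

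Section 4.1.3 refers to the Compound Level Safety Standard for further detail on baseline and post-baseline definitions.

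**The concern.** The baseline rule treats first exposure during the Maintenance Period as if it always happened at Week 16. For a placebo responder who escapes later, the Week 16 injection is placebo (Protocol Section 6.1, Table 2), and weeks or months of placebo treatment follow before any lebrikizumab. An event that begins in that interval is new relative to the stated baseline and lies inside the Treatment Period, so the SAP text lets it count as a lebrikizumab TEAE.

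The SAP recognises this placebo time elsewhere, since Section 4.6.1 removes it from exposure. Section 4.1.2 also keeps MSP data up to the time of escape, and the AE table list in Section 4.6.2 gives the MSP its own AE overview. One placebo-period event could therefore appear under placebo in the MSP overview and under Any Lebrikizumab in the pooled tables.

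What is at stake is correct attribution in the pooled safety tables, which Section 4.8 places in the Week 52 analysis for the initial Japanese submission. Tables with few events, such as SAEs or special topics, are the most sensitive to one or two misplaced cases.

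**Working it through.** **Inputs**

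- Arm sizes 120, 80 and 80; assumed placebo response 20% for EASI-75 and 13% for IGA 0/1 (SAP Section 5, Protocol Section 9.2).
- Late escape visits: every 4 weeks from Week 20 to Week 64, 12 visits (SAP Section 1.2, Protocol Section 4.1).
- Maintenance Period: Week 16 to Week 68 (SAP Section 4.1.2).
- Share of placebo responders who escape late: not given. I assume 10–50% and ignore dropout.

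The plan gives no figure of its own on this point. The response rates come from its power statement, which does reproduce. An exact two-sided Fisher test at 0.05 gives power of 0.9795 (IGA) and 0.9998 (EASI-75) for Q2W, and 0.8254 and 0.9906 for Q4W, against the stated >95% and >80%.

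**Step 1: the two windows for one late escaper.** For escape at Week e, placebo time after the TEAE baseline is e − 16 weeks and lebrikizumab exposure to Week 68 is 68 − e weeks. The TEAE window as written is 68 − 16 = 52 weeks.

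| Escape week | Placebo weeks after baseline | Lebrikizumab weeks | TEAE window / exposure |
|---|---|---|---|
| 20 | 4 | 48 | 52/48 = 1.08 |
| 40 | 24 | 28 | 52/28 = 1.86 |
| 52 | 36 | 16 | 52/16 = 3.25 |
| 64 | 48 | 4 | 52/4 = 13 |

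If escapes spread evenly over the 12 visits, the mean escape week is 42 and the mean placebo time is 26 weeks. For a Week 16 escaper, e − 16 = 0 and the windows agree, so the rule is right for that group.

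**Step 2: how many people.** Staying on placebo requires EASI-75 and/or IGA 0/1.

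- Full overlap of the two responses: 80 × 0.20 = 16.
- No overlap: 80 × (0.20 + 0.13) = 26.4, about 26.
- Late escapers: 16 × 0.10 = 1.6 up to 26 × 0.50 = 13, so about 2–13 people.
- Pooled population, 200 + (80 − R) + L for R responders and L late escapers: about 257 to 272. Late escapers make up 0.6% to 4.9% of it.

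**Step 3: how much placebo time.** Placebo weeks = L × (e − 16). Lebrikizumab weeks = 200 × 68 + (80 − R) × 52 + L × (68 − e). With e = 42:

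- R = 16, 25% escaping, L = 4: 4 × 26 = 104 placebo weeks (2.0 person-years) against 13,600 + 3,328 + 104 = 17,032 lebrikizumab weeks (326.4 person-years), a ratio of 0.6%.
- R = 26, 50% escaping, L = 13: 13 × 26 = 338 placebo weeks (6.5 person-years) against 13,600 + 2,808 + 338 = 16,746 lebrikizumab weeks (320.9 person-years), a ratio of 2.0%.

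Across the extremes (10% to 100% escaping, all at Week 20 or all at Week 64) the ratio runs from 0.04% to 7.6%.

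**Step 4: one participant followed through the text.** A placebo responder has an event starting at Week 30 and escapes at Week 44. The event was not ongoing at Week 16, so it is new after the Section 4.1.2 baseline. Section 4.6.2 counts it within the Treatment Period. Section 4.6.1 starts this person's lebrikizumab exposure at Week 44. Nothing in the SAP removes the event from the pooled lebrikizumab tables.

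**The case against.** The strongest reply is that a baseline is only half of the definition. A Week 30 placebo event becomes a lebrikizumab TEAE only if it also falls in the post-baseline window, and Section 4.1.3 refers to the Compound Level Safety Standard for more detail on that. Section 4.6.3.4 places the full derivation rules for special topics there too, and lets topic changes documented there supersede the SAP. Section 4.6.1 also works by treatment periods in which the participant receives lebrikizumab. If Section 4.6.2 means the same by Treatment Period, the placebo event drops out. This stands as a limit on certainty: it cannot be said that these events will be counted. It does not rescue the stated rule, because the SAP sets the Week 16 baseline outright and nowhere starts the window at the first lebrikizumab dose.

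Four stronger readings are tempting, and the documents do not support them.

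- **That AE rates are distorted because numerator and denominator differ.** Section 4.6.2 plans numbers and percentages of participants, and the SAP names no exposure-adjusted AE rate. The mismatch arises only when AE counts are read beside the exposure table.
- **That low-count topics will shift by several cases.** The documents give no placebo event rate. At 26 weeks each, 2–13 people contribute about 1.0–6.5 placebo person-years, so three extra cases in one topic would need 3/6.5 ≈ 0.5 to 3/1.0 = 3 events per person-year.
- **That AD exacerbation will be systematically inflated.** Escape is triggered by loss of EASI-50, not by an adverse event. Protocol Section 10.3.1 excludes expected signs of the studied disease unless they are more severe than expected, although its text on lack of efficacy points the other way.
- **That the escape analysis is invalid or its Total column wrong.** Section 3 already shows the placebo-to-lebrikizumab group separately and without comparisons. The stated aim, "to assess whether these participants re-gain EASI-50 response or achieve a higher level of response (for example, EASI-75) following re-treatment", fits placebo responders in its first part, since they generally had and then lost EASI-50. Only the word re-treatment is inaccurate for people never treated before.

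**Conclusion.** The baseline rule in SAP Section 4.1.3, carried into 4.1.4, is wrong as written for one subgroup, and the impact is modest. It leaves 4 to 48 placebo weeks per late escaper inside the TEAE window while Section 4.6.1 leaves them out of exposure.

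The 16–26 responders rest on the planned response rates, and the 2–13 affected people also rest on an assumed 10–50% late escape. The number of misattributed cases cannot be computed from the documents. Events already ongoing at Week 16 at unchanged severity are not affected. Any error would add events to the lebrikizumab column rather than hide them, in a descriptive pooled group.

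The placebo-controlled Induction safety comparison, the Maintenance Primary Population tables and the co-primary analyses are unaffected. A reader might infer that the pooled safety conclusion is unreliable. At this size, and with the Standard unseen, that goes too far. The point should be corrected before the pooled tables are produced.

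**What to change.** In SAP Sections 4.1.3 and 4.1.4, state that for participants who switch from placebo to lebrikizumab, the TEAE baseline is the period up to the first lebrikizumab injection, and only events that start or worsen on or after that date are counted. That is the date Section 4.6.1 already uses, and it leaves the anchor date of Week 16 escapers where it is.

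Apply the same anchor to the categorical laboratory and vital-sign changes. Section 4.1.3 plans these for the same population but specifies a baseline only for TEAEs. Check the wording against the Compound Level Safety Standard so that the two agree; if the Standard already uses this window, the SAP sentence should say so.

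For the W20-64 Escape analysis, at most correct the re-treatment label for the placebo-to-lebrikizumab group in Section 3 and the matching Appendix 2 rows. The Total column can stay.

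The cost is one sentence and one derivation rule. Injection dates are already recorded, so no new data are needed and no participants are lost.

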4.1.5. Adjustments for Covariates

Unless otherwise specified, the statistical analysis models for the Induction Period efficacy and health outcome analysis will include the following stratification factors for Baseline randomization: age (adolescent participants 12 to <18 versus adults ≥ 18 years) and baseline disease severity (IGA 3 versus 4).

In general, when an MMRM is to be used for analyses, baseline value and baseline-by-visit interactions will be included as covariates; when an ANCOVA is to be used for analyses, baseline value will be included as a covariate.

4.1.6. Handling of Dropouts or Missing Data

Depending on the estimand being addressed, different methods will be used to handle missing data. Description of the estimands can be found in Section 1.1.1.

4.1.6.1. Handling of Dropouts or Missing Data for Induction Period

For efficacy analysis relative to the primary estimand, missing data including those as a result of intercurrent events will be imputed based on Markov chain Monte Carlo Multiple Imputation (MCMC-MI). The description of MCMC-MI method can be found in Section 4.1.6.1.1. Tipping point analysis as described in Section 4.1.6.1.2 will serve as the sensitivity analysis for the primary analysis.

For efficacy analysis relative to the supportive estimand for categorical endpoints, missing data including those as a result of intercurrent events will be imputed as non-responder. The description of non-responder imputation (NRI) can be found in Section 4.1.6.1.3.

For efficacy analysis relative to the supportive estimand for continuous endpoints collected multiple times post-baseline, a Mixed-effects Model for Repeated Measures (MMRM) will be performed without explicit imputation. The description of MMRM can be found in Section 4.1.6.1.4.

For efficacy analysis relative to the supportive estimand for continuous endpoints collected only once post-baseline, missing data including those as a result of intercurrent events will be imputed using Last Observation Carried Forward (LOCF). The description of LOCF can be found in Section 4.1.6.1.5.

The table below describes the planned imputation methods for efficacy and health outcome endpoints.

Imputation Techniques for Various Variables during Induction Period

Type of Endpoints	Efficacy and Health Outcome Endpoints	Estimand (Analysis strategy for Intercurrent Events)	Missing Data Imputation Method (Analysis Method)
Categorical		Primary Estimand (Hybrid)	MCMC-MI,

	IGA, EASI, and Itch NRS related categorical endpoints at pre-specified timepoints		Tipping point analysis (CMH)
		Supportive Estimand (Composite)	NRI (CMH)
	Remaining categorical endpoints	Supportive Estimand (Composite)	NRI (CMH)
Continuous	EASI percentage change, Itch NRS percentage change	Primary Estimand (Hybrid)	MCMC-MI (ANCOVA)
		Supportive Estimand (Hypothetical)	No imputation (MMRM)
	Remaining continuous endpoints at multiple post-baseline timepoints	Supportive Estimand (Hypothetical)	No imputation (MMRM)
	Remaining continuous endpoints collected only once post-baseline	Supportive Estimand (Hypothetical)	LOCF (ANCOVA)

Abbreviations: ANCOVA = analysis of covariance; CMH = Cochran-Mantel-Haenszel; EASI = Eczema Area and Severity Index; IGA = Investigator's Global Assessment for AD; LOCF = last observation carried forward; MCMC-MI = Markov chain Monte Carlo multiple imputation; MMRM = mixed-effects model for repeated measures; NRI = Non-Responder Imputation; NRS = Numeric Rating Scale.

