1.1.1.3. Supportive Estimand for Continuous Endpoints (Hypothetical)

The supportive estimand for continuous endpoints is a hypothetical estimand representing the supportive clinical question of interest: what is the difference between treatment conditions in the target participant population, in means after 16 weeks if rescue medication was not available and all participants adhered to the treatment?

The supportive estimand is described by the following attributes:

- A. Population: defined through appropriate I/E criteria to reflect the targeted participant population for approval
- B. Endpoint: apply to all continuous endpoints
- C. How to account for ICEs

- a. For participants who require any use of rescue medication or discontinued treatment prior to Week 16, a hypothetical strategy will be used to estimate what the treatment effect would have been if rescue medication was not available and all participants adhered to the treatment. Therefore, hypothetical strategy is used for these types of ICEs.

D. Population-level summary: difference in means between treatment conditions

Details on how missing data including those as a result of intercurrent events will be handled can be found in Section 4.1.6.1. Detailed analyses relative to estimands including analysis type, method and imputation, population, time point, and treatment comparisons for efficacy and health outcome analyses can be found in [Appendix 2](#).

The table below summarizes the analytical strategies that will be conducted on the intercurrent events for the three estimands.

Description of Primary and Supportive Estimands for Induction Period

Estimand	Analysis Strategy for Intercurrent Events			Missing Data Imputation Method	
	Rescue Medication	Treatment Discontinuation			
		Due to lack of efficacy	Due to any other reasons		
Primary Estimand (Hybrid)	Composite: Set to baseline	Composite: Set to baseline	Hypothetical: Set to missing	Primary analysis: MCMC-MI	
	Composite: Set to baseline	Composite: Set to baseline	Hypothetical: Set to missing	Sensitivity analysis Tipping point analysis	
Supportive Estimand for Categorical Endpoints (Composite)	Composite: Set to non-responder	Composite: Set to non-responder	Composite: Set to non-responder	Supplementary analysis: NRI	
Supportive Estimand for Continuous Endpoints (Hypothetical)	Hypothetical: Set to missing	Hypothetical: Set to missing	Hypothetical: Set to missing	Supplementary analysis MMRM/LOCF	

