4.1.6.1.5. Last Observation Carried Forward (LOCF)

In this analysis, the values subsequent to rescue medication use (i.e., high-potency TCS or systemic AD treatment, defined in [Appendix 13](#)) or treatment discontinuation will be made missing. All missing values will be imputed using LOCF. Baseline value will be used for imputation if there is no post-baseline observation.

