4.9. Changes to Protocol-Planned Analyses

- Removed analysis for other secondary endpoint of “Number of Skin Pain-Free (Skin Pain NRS = 0) days”
- Updated definition of analysis population for the Maintenance Period

5. Sample Size Determination

Approximately 280 participants will be randomized at a 3:2:2 ratio to lebrikizumab 250 mg Q2W, lebrikizumab 250 mg Q4W, or placebo (120 participants: 80 participants: 80 participants). The inclusion of approximately 15 adolescents is based on enrollment feasibility in Japan.

The assumed IGA score of 0 or 1 at Week 16 response rates are 38% for lebrikizumab 250 mg Q2W, 33% for lebrikizumab 250 mg Q4W, and 13% for placebo. The assumed EASI-75 response rates at Week 16 are 58% for lebrikizumab 250 mg Q2W, 53% for lebrikizumab 250 mg Q4W, and 20% for placebo. The assumptions for lebrikizumab are based on the DRM06-AD01 Phase 2b study, and the proportion of participants who achieved an IGA score of 0 or 1 and proportion of participants who achieved EASI-75 response at Week 16 using the rescue medication non-response sensitivity analysis, adjusting for the allowed use of TCS. The placebo response rate is based on the review of historical TCS clinical studies in AD (Simpson et al. 2016). This study has >95% and >80% power to test the superiority of lebrikizumab 250 mg Q2W to placebo and lebrikizumab 250 mg Q4W to placebo in the co-primary endpoints based on a two-sided Fisher exact test with alpha of 0.05.

6. Supporting Documentation

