		Maintenance Supportive Estimand (Hypothetical)	Descriptive statistics with LOCF	MPP with self-reported comorbid asthma	No comparisons. All scheduled visits in the Maintenance Period	Secondary analysis
Topical corticosteroid (TCS) or topical calcineurin inhibitor (TCI) Use	Time (days) to TCS/TCI-free use from Baseline to Week 16	N/A	KM method with log-rank test	ITT	Leb 250 mg Q2W vs PBO; Leb 250 mg Q4W vs PBO;	Secondary analysis
	Time (days) to TCS/TCI-free use from Baseline to Week 68	N/A	KM method	MPP	No comparisons.	Secondary analysis
	Proportion of TCS/TCI-free days from Baseline to Week 16	N/A	Descriptive statistics with observed data Two-sample t-test and ANOVA including treatment group and stratification factors with observed data	ITT	Leb 250 mg Q2W vs PBO; Leb 250 mg Q4W vs PBO; Baseline through Week 16 in the Induction Period	Secondary analysis

Measure	Variable	Estimand (Section 1.1.1)	Analysis Method (Section 4.1)	Population (Section 3)	Comparison/Time Point	Analysis Type
	Proportion of TCS/TCI-free days from Baseline to Week 68	N/A	Descriptive statistics with observed data	MPP	No comparisons. Baseline through Week 68 in the Combined Induction and Maintenance Periods	Secondary analysis
	Mean weight of TCS use by potency (tube weights) from Baseline to Week 16	N/A	Descriptive statistics with observed data Two-sample t-test and ANOVA including treatment group and stratification factors with observed data	ITT	Leb 250 mg Q2W vs PBO; Leb 250 mg Q4W vs PBO; Baseline through Week 16 in the Induction Period	Secondary analysis
	Mean weight of TCS use by potency (tube weights) from Baseline to Week 68	N/A	Descriptive statistics with observed data	MPP	No comparisons. Baseline through Week 68 in the Combined Induction and Maintenance Periods	Secondary analysis
Thymus and activation-regulated chemokine (TARC)	Observed TARC value	N/A	Descriptive statistics and box plots with observed data	ITT	No comparisons. All scheduled visits in the Induction Period	Secondary analysis
				MPP	No comparisons. All scheduled visits in the Maintenance Period	Secondary analysis
	Change from baseline in TARC	N/A	Descriptive statistics and box plots with observed data ANCOVA with LOCF	ITT	Leb 250 mg Q2W vs PBO; Leb 250 mg Q4W vs PBO; Week 16 and all scheduled visits in the Induction Period	Secondary analysis

Measure	Variable	Estimand (Section 1.1.1)	Analysis Method (Section 4.1)	Population (Section 3)	Comparison/Time Point	Analysis Type

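### ACQ-5 has a hypothetical estimand, but its LOCF analysis in practice sets affected participants to baseline; separately, TARC gets LOCF where the SAP's own rule for repeated measures is MMRM

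*SAP*

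**What the plan says.** **ACQ-5.** SAP 1.1.1.3 gives continuous endpoints a hypothetical supportive estimand. For rescue and discontinuation the strategy is "to estimate what the treatment effect would have been if rescue medication was not available and all participants adhered to the treatment". SAP 4.1.6.1 then chooses the method by number of visits. Endpoints with several post-baseline measurements get MMRM without imputation. For endpoints with only one, "missing data including those as a result of intercurrent events will be imputed using Last Observation Carried Forward (LOCF". SAP 4.1.6.1.5 makes values after rescue or treatment discontinuation missing before carrying forward, and adds: "Baseline value will be used for imputation if there is no post-baseline observation". Appendix 2 (SAP 6.2) places the Week 16 change in ACQ-5 under the hypothetical estimand, analysed by "ANCOVA with LOCF" in ITT participants with self-reported asthma. The Schedule of Activities (Protocol 1.3) has ACQ-5 at screening, Week 0 and Week 16 of the Induction Period.

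**TARC.** The Schedule of Activities has TARC at Week 0 and at Weeks 4, 8, 12 and 16. SAP 4.1.1, and the row for repeatedly measured continuous endpoints in the 4.1.6.1 table, prescribe MMRM for such variables. Appendix 2 lists the TARC estimand as N/A. It plans observed-data summaries and box plots, plus "ANCOVA with LOCF" for the comparisons with placebo.

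**The concern.** The estimand table that closes SAP 1.1.1.3 distinguishes two operations. Setting a value to missing is labelled hypothetical; setting it to baseline is labelled composite. With a single post-baseline visit, setting to missing and then applying LOCF gives the same number as setting to baseline. The ACQ-5 analysis therefore carries a hypothetical label but does what the SAP itself calls composite.

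This goes beyond participants who miss Week 16. Under Protocol 6.5.3, a participant who needs systemic rescue stops study intervention but keeps attending visits through Week 16. That participant may have an observed Week 16 ACQ-5 score, which is deleted and replaced by baseline.

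ACQ-5 change to Week 16 is an other secondary endpoint in Protocol Section 3. It will be reported with a treatment difference, confidence interval and p-value (SAP 4.1.1). A reader would take that difference as the effect without rescue and with full adherence.

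For TARC the problem is different. Appendix 2 departs from the SAP's general rule for repeated measurements and gives no reason.

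**Working it through.** **Plan's own figures.** The documents give no ACQ-5 or TARC effect, SD, asthma prevalence or missingness rate, so there is no figure on this point to reproduce. The only design figure is the power in SAP Section 5, for the co-primary endpoints. With 120, 80 and 80 participants, exact two-sided Fisher power is 0.9795 (Q2W, IGA), 0.9998 (Q2W, EASI-75), 0.8254 (Q4W, IGA) and 0.9906 (Q4W, EASI-75). This agrees with the stated >95% and >80%, and the present point does not touch it.

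**Step 1: scheduled post-baseline Induction visits.**
- ACQ-5: Week 16 only, so 1.
- TARC: Weeks 4, 8, 12 and 16, so 4.

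**Step 2: follow the ACQ-5 rule for a rescued or discontinued participant.**
1. The Week 16 value, if any, falls after the event and is made missing (4.1.6.1.5).
2. No earlier scheduled post-baseline value exists.
3. Baseline is used, so the change is baseline minus baseline = 0.

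A participant with no event but a missing Week 16 score also gets 0.

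**Step 3: effect on the estimate.** Let m be the share of an arm set to baseline and d the arm's true mean change. Assume that those set to baseline would have changed by d on average, like the rest. The expected arm mean is then (1 - m) x d, and the expected difference is

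(1 - m_active) x d_active - (1 - m_placebo) x d_placebo.

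All inputs below are assumptions. The value 0.5 is used for scale because SAP Appendix 1 takes it as the ACQ-5 minimal clinically important difference.

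| d active | d placebo | m active | m placebo | True difference | LOCF difference |
|---|---|---|---|---|---|
| -0.5 | 0 | 5% | 5% | -0.50 | 0.95 x (-0.5) - 0 = -0.475 |
| -0.5 | 0 | 10% | 10% | -0.50 | 0.90 x (-0.5) - 0 = -0.45 |
| -0.5 | 0 | 20% | 20% | -0.50 | 0.80 x (-0.5) - 0 = -0.40 |
| -0.5 | -0.5 | 10% | 30% | 0 | -0.45 - (-0.35) = -0.10 |
| -0.5 | -0.25 | 10% | 30% | -0.25 | -0.45 - (-0.175) = -0.275 |
| -0.5 | -0.25 | 30% | 10% | -0.25 | -0.35 - (-0.225) = -0.125 |

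Equal shares shrink the difference. Unequal shares can create a difference where none exists, enlarge a true one, or halve it. The spurious -0.10 is 0.10 / 0.5 = 20% of the minimal clinically important difference.

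**Step 4: TARC against the SAP's practice elsewhere.** WPAI-AD has two post-baseline Induction visits (Weeks 8 and 16) and gets MMRM in Appendix 2. TARC has four and gets LOCF.

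**The case against.** **What stands.** LOCF for once-measured endpoints is a deliberate rule, stated consistently in the estimand table, 4.1.6.1, 4.1.6.1.5 and Appendix 2. The ACQ-5 fault is a mismatch between estimator and estimand, not contradictory text. For TARC, the sentence on the supportive estimand does not strictly bind an analysis whose estimand is N/A. TARC is also a pharmacodynamic measure (Protocol 8.6) and is absent from the endpoint lists in both documents. The conflict is with the general rule in 4.1.1 and the 4.1.6.1 table row. Neither measure is in the multiplicity-controlled family, ACQ-5 concerns only the asthma subset, and Protocol 7.2 expects discontinuation to be uncommon.

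**Stronger readings that a reader might infer, and that do not hold.**
- *The interval is too narrow because imputed zeros count as observed.* Baseline carried forward is a deterministic function of recorded data, so the ANCOVA standard error describes the sampling variability of that estimator. In simulations under assumed inputs (30 vs 20 or 60 vs 40 participants, SD 0.8, baseline correlation 0.5, 5-20% missing at random), the model standard error matched the empirical SD, for example 0.196 against 0.194. Coverage below 95% came from bias.
- *Every affected participant always gets exactly zero.* SAP 4.1.1 lets unscheduled in-period assessments feed LOCF, so one taken before the event could be carried forward. ACQ-5 is also scheduled at Visit 24/ET, although an early-termination value after treatment discontinuation would be deleted.
- *The estimate shrinks by a known percentage.* That needs missingness rates the documents do not give, and the assumption that affected participants resemble the others.

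**Conclusion.** The ACQ-5 point holds. Followed as written, the SAP estimates something close to a composite effect under a hypothetical label, and the resulting bias has no fixed direction, so LOCF cannot be defended here as conservative. The -0.10 example and the other rows are illustrations; the real size depends on how many asthma participants are rescued, stop or miss Week 16 in each arm. The conclusion itself rests only on the visit schedule, the deletion rule and the SAP's own strategy labels.

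The TARC point holds as a separate internal inconsistency: four post-baseline visits, a general MMRM rule, and an unexplained LOCF analysis for the comparisons with placebo.

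Both are minor. Sample size, power and the co-primary and key secondary analyses are unaffected.

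**What to change.** **ACQ-5.** In SAP 4.1.6.1 (text and table), the estimand table and Appendix 2, replace LOCF by ANCOVA on Week 16 values not affected by intercurrent events, with treatment, baseline and stratification factors as in 4.1.1. State the assumption: missing at random given baseline and strata. It deserves a caveat, because Protocol 6.5.1 treats systemic corticosteroids given for an asthma exacerbation as rescue, so some deletions may relate to the outcome. LOCF can stay as a sensitivity analysis.

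Alternatively, keep the method and relabel the ACQ-5 estimand as composite, saying that rescue and discontinuation for any reason count as no change. The treatment of Week 16 values missing without such an event must then be stated too.

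Do not reuse the multiple imputation in 4.1.6.1.1 as written. It first sets rescued and lack-of-efficacy participants to baseline, which brings back the same mismatch.

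**TARC.** Use the MMRM in 4.1.1 for the comparisons with placebo and keep the observed-data summaries.

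**Cost.** SAP wording only, since ANCOVA and MMRM are already specified. Intervals on these two non-key measures become somewhat wider.
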